15.6.4. Safety

Adverse Events
AE up to Week 4

 • Cut-off date of Week 4 for individuals will be based on Week 4 visit date which is associated with the earliest date throughout Week 4 records (i.e., SDTM.SVSTDTC).
AEs of Special Interest (AESIs)

AESIs are manually-selected at patient-level (i.e. following case-by-case review by members of the SRT including representatives from the local Japan team) and not at preferred term level.
 
AESI categories are classified as follows:
 
 • Thrombosis and/or tissue ischemia secondary to excessive erythropoiesis • Death, myocardial infarction, stroke, heart failure, thromboembolic events, thrombosis of vascular access • Cardiomyopathy • Pulmonary artery hypertension • Cancer-related mortality and tumor progression and recurrence • Esophageal and gastric erosions • Proliferative retinopathy, macular edema, choroidal neovascularization • Exacerbation of rheumatoid arthritis 
Following events will be programmatically identified as AESIs.
 
Thrombosis and tissue ischemia events will be considered to be secondary to excessive erythropoiesis if during the window of [AE start date – 30 days, AE start date +15 days] any one of the following 3 events occurs:
 
 • Any Hgb value > 13 g/dL • Hgb increase > 2 g/dL over 2 weeks (applied to only Cohort 3) • Hgb increase > 4 g/dL over 4 weeks 
Note: Thrombosis and tissue ischemia events that need to be considered against the above 3 Hgb events will be identified by the case-by-case review.
 
Note: HemoCue and central laboratory values will be considered separately. Unscheduled Hgb values will also be used in the assessment of secondary to excessive erythropoiesis if available.
 
Note: All Hgb values that have an assessment date within the window of [AE start date – 58 days, AE start date + 15 days] will be considered.
 
Any SAE which outcome is fatal will be identified AESI as death.

CV Events

Patient profiles of CV events will be provided according to records captured in eCRF, except for Peripheral Arterial Thrombosis Embolism (PAT) form.
 
CV events in PAT form will be provided only when a related AE sequence number is not present. This is because several records in PAT form are captured just for AESI information instead of CV events.

Laboratory Parameters

- LDL/HDL cholesterol ratio will be derived from the following equation.
 - $\text{LDL/HDL cholesterol ratio} = \text{LDL cholesterol (mmol/L)} / \text{HDL cholesterol (mmol/L)}$

Laboratory Parameters
Imputation

 If a laboratory value which is expected to have a numeric value for summary purposes, has a non-detectable level reported in the database, where the numeric value is missing, but typically a character value starting with '<x' or '>x' (or indicated as less than x or greater than x in the comment field) is present, the number of significant digits in the observed values will be used to determine how much to add or subtract in order to impute the corresponding numeric value. 
 Example 1: 2 Significant Digits = '< x' becomes $x - 0.01$ Example 2: 1 Significant Digit = '> x' becomes $x + 0.1$ Example 3: 0 Significant Digits = '< x' becomes $x - 1$ The following laboratory values will not be applicable for this imputation: 
 Hgb, serum iron, serum ferritin, serum transferrin, TIBC, UIBC, TSAT, and Hepcidin The default convention for reporting of clinical laboratory units will be the international system of units (SI units).
Log-transformation

 Lipid parameters will be log-transformed and the percent change from baseline will be reported. Based on literature review the distributions of hepcidin and TSAT are skewed and require a log-transformation. Other endpoints may also be log-transformed if deemed appropriate (See Section 5.2).
Others

 For summaries of, the absolute neutrophils and lymphocytes count, PCI cutoffs will be calculated by multiplying the percentages given for each subject by the absolute white blood count.

15.6.5. Pharmacokinetic

General
Dose level

 Summaries by dose level and used tablet strength will be based on an actual dose associated with a container number (See Section 15.6.2). Tablet strength is defined as follows: 
 Actual dose = 1 mg → 1 mg tablet strength Actual dose = 2 mg → 2 mg tablet strength Actual dose = 4 mg → 4 mg tablet strength Actual dose = 6 mg → 6 mg tablet strength Actual dose = 8 mg → 4 mg tablet strength Actual dose = 12 mg → 6 mg tablet strength Actual dose = 18 mg → 6 mg tablet strength Actual dose = 24 mg → 6 mg tablet strength Dose level which is actually provided to subjects will be derived from an actual dose of the visit (including unscheduled visit) which meets the following: 
 Treatment Start Date ≤ Date of last dose taken prior to PK sampling ≤ Treatment Stop Date
Others

 Dose normalized PK parameters will be derived from the PK parameters dividing by actual dose (mg). In aggregated analyses, data collected in Week 12 and Week 24 will be aggregated. For the PK parameters calculation, the concentration at 0 hr will be set to 0 and assign zero to NQ values. Individual's PK parameters calculated less than 4-time point concentrations, or any time deviated (beyond ± 30 min of scheduled visits) concentrations, or concentrations obtained in the less interval of last two treatment administrations than 12 hours will be omitted from summaries and figures. but

General
presenting in a listing.

15.6.6. Exploratory Endpoint

CKD Progression
Equation for eGFR
eGFR is estimated by the following Japanese Society of Nephrology-Chronic Kidney Disease Initiatives (JSN-CKDI) equation. Male: $eGFR \text{ (mL/min/1.73m}^2\text{)} = 194 * \text{Serum creatinine}^{-1.094} * \text{Age}^{-0.287}$ Female: $eGFR \text{ (mL/min/1.73m}^2\text{)} = 194 * \text{Serum creatinine}^{-1.094} * \text{Age}^{-0.287} * 0.739$
eGFR decrease of 30% or more from baseline
eGFR decrease of 30% or more from baseline is defined as follows. At each assessment visit, $eGFR \text{ change (\%)} = (eGFR - \text{Baseline eGFR}) / \text{Baseline eGFR} * 100$ If eGFR change (%) < -30 then let the eGFR at the visit be decrease of 30% or more from baseline.
Serum creatinine increase of more than double from baseline
Serum creatinine increase of more than double from baseline is defined as follows. At each assessment visit, $\text{Serum creatinine change (\%)} = (\text{Serum creatinine} - \text{Baseline serum creatinine}) / \text{Baseline serum creatinine} * 100$ If Serum creatinine change (%) > 200 then let the Serum creatinine at the visit be increase of more than double from baseline.

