7.4.2. Summary Measure

- **CKD progression (eGFR, serum creatinine, urine creatinine, urine albumin, urine albumin/creatinine ratio)**

Raw observed value at each assessment visits

The values will be summarized using mean, standard deviation, 95%CI, minimum, P25, median, P75, and maximum at each assessment visit by treatment group. Graphical summaries will be provided using mean and 95% CI over time.

Change from baseline at each assessment visit

The values will be summarized using mean, standard deviation, 95%CI, minimum, P25, median, P75, and maximum at each assessment visit by treatment group. Graphical summaries will be provided using mean and 95% CI over time.

Number (%) of subjects with eGFR decrease of 30% or more from baseline

The number and percentage of subjects with eGFR decrease of 30% or more from baseline will be summarized at each assessment visit by treatment group.

Number (%) of subjects with serum creatinine increase of more than double from baseline

The number and percentage of subjects with serum creatinine increase of more than double from baseline will be summarized at each assessment visit by treatment group.

- **Other**

Scatter plot of change from baseline in Hgb at Week 4 vs. covariates of interest

Scatter plot of change from baseline in Hgb at Week 4 versus following covariates of interest, body weight, baseline Hgb, prior ESA dose will be produced for the ITT and Efficacy PD populations. See Section 15.6.3 for the detailed derivations.

Scatter plot of mean dose during Week 40 to 52 vs. covariates of interest

Scatter plot of mean dose during Week 40 to 52 versus following covariates of interest, body weight, baseline Hgb, prior ESA dose will be produced for the ITT and Efficacy PD populations. See Section 15.6.3 for the detailed derivations.

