2.118.	ITT	EFF_T18	Summary of Hepcidin (nmol/L) by Visit by Subgroup - ITT	baseline iron use, prior ESA use	Y
2.119.	Efficacy PD	EFF_T18	Summary of Hepcidin (nmol/L) by Visit by Subgroup – Efficacy PD	baseline iron use, prior ESA use	Y
2.120.	ITT	EFF_T19	Summary of Hepcidin (nmol/L) Percent Change from Baseline by Visit by Subgroup — ITT	baseline iron use, prior ESA use	Y
2.121.	Efficacy PD	EFF_T19	Summary of Hepcidin (nmol/L) Percent Change from Baseline by Visit by Subgroup – Efficacy PD	baseline iron use, prior ESA use	Y
2.122.	ITT	LB1	Summary of Serum Iron (umol/L) by Visit by Subgroup - ITT	baseline iron use, prior ESA use	Y
2.123.	Efficacy PD	LB1	Summary of Serum Iron (umol/L) by Visit by Subgroup – Efficacy PD	baseline iron use, prior ESA use	Y
2.124.	ITT	LB1	Summary of Serum Iron (umol/L) Change from Baseline by Visit by Subgroup - ITT	baseline iron use, prior ESA use	Y
2.125.	Efficacy PD	LB1	Summary of Serum Iron (umol/L) Change from Baseline by Visit by Subgroup – Efficacy PD	baseline iron use, prior ESA use	Y

CONFIDENTIAL

201753

Efficacy: Tables					
No.	Population	IDSL / Example Shell	Title	Programming Notes	SAC
2.126.	ITT	LB1	Summary of Total Iron Binding Capacity (umol/L) by Visit by Subgroup - ITT	baseline iron use, prior ESA use	Y
2.127.	Efficacy PD	LB1	Summary of Total Iron Binding Capacity (umol/L) by Visit by Subgroup – Efficacy PD	baseline iron use, prior ESA use	Y
2.128.	ITT	LB1	Summary of Total Iron Binding Capacity (umol/L) Change from Baseline by Visit by Subgroup - ITT	baseline iron use, prior ESA use	Y
2.129.	Efficacy PD	LB1	Summary of Total Iron Binding Capacity (umol/L) Change from Baseline by Visit by Subgroup – Efficacy PD	baseline iron use, prior ESA use	Y
CKD Progression					
2.130.	ITT	LB1	Summary of CKD Progression by Visit		Y
2.131.	ITT	LB1	Summary of CKD Progression Change from Baseline by Visit		Y
2.132.	ITT	EFF_T20T20	Summary of Number (%) of Subjects with eGFR Decrease of 30% or More from Baseline		Y
2.133.	ITT	EFF_T20T20	Summary of Number (%) of Subjects with Serum Creatinine Increase of More Than Double from Baseline		Y

CONFIDENTIAL

201753

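### The serum creatinine doubling flag in SAP section 15.6.6 is set at a change above 200%, which is more than tripling, so Table 2.133 would undercount the event it names

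*SAP*

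**What the plan says.** Section 7.4.2 names two subject counts among the CKD progression displays. For creatinine: "The number and percentage of subjects with serum creatinine increase of more than double from baseline will be summarized at each assessment visit". For eGFR: "The number and percentage of subjects with eGFR decrease of 30% or more from baseline will be summarized at each assessment visit by treatment group". Section 7.4.1 lists both under the same names. In section 15.10.4.2 the creatinine count becomes Table 2.133 in the ITT population, titled "Summary of Number (%) of Subjects with Serum Creatinine Increase of More Than Double from Baseline"; the eGFR count is Table 2.132.

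Section 15.6.6 holds the derivations. Each change is a relative change in percent: visit value minus baseline, divided by baseline, times 100. The flags are then:

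- creatinine: "If Serum creatinine change (%) > 200 then let the Serum creatinine at the visit be increase of more than double from baseline"
- eGFR: "If eGFR change (%) < -30 then let the eGFR at the visit be decrease of 30% or more from baseline"

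No other section gives a different derivation or corrects either cut-off.

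**The concern.** The number 200 suits a quantity expressed as a percentage of baseline, where a doubled value is 200%. The SAP's quantity has baseline subtracted, so a doubled value is 100%. The label and the programmed rule therefore describe different events.

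Programmed as written, the table would carry a doubling title and a tripling count. Nothing in the title or the numbers would tell a reader of the study report that the definition had shifted.

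The eGFR flag has a smaller fault of the same kind: an inclusive label and a strict inequality.

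**Working it through.** **Inputs**

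- Event names: creatinine more than double baseline; eGFR down by 30% or more (sections 7.4.1, 7.4.2, 15.10.4.2).
- Change formula and flags: above 200 for creatinine, below -30 for eGFR (section 15.6.6).
- eGFR equation: proportional to creatinine to the power -1.094, with an age term and a sex factor (section 15.6.6).

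**Step 1. The SAP's cut-off as a ratio.** Let r = visit value / baseline. Then change (%) = (r - 1) × 100.

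- Change > 200 gives r - 1 > 2, so r > 3.
- The named event, r > 2, gives change > (2 - 1) × 100 = 100.

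The stated 200 cannot be reproduced as the threshold for more than double. It would be right only for r × 100, with no baseline subtracted.

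**Step 2. Values on either side.** The eGFR column is (r^-1.094 - 1) × 100, with age held fixed.

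| r | Change (%) | More than double? | Flag as written (> 200) | Flag at > 100 | eGFR change (%) |
|---|---|---|---|---|---|
| 1.5 | 50 | no | no | no | -35.8 |
| 2.0 | 100 | no | no | no | -53.2 |
| 2.01 | 101 | yes | **no** | yes | -53.4 |
| 2.5 | 150 | yes | **no** | yes | -63.3 |
| 3.0 | 200 | yes | **no** | yes | -69.9 |
| 3.01 | 201 | yes | yes | yes | -70.0 |

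The misclassified group is exactly 2 < r ≤ 3. An exact doubling is outside the named event under either cut-off, so it is not part of the error.

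As a made-up example, a rise from 3.0 to 8.9 mg/dL is (8.9 - 3.0) / 3.0 × 100 = 196.7%. The value is nearly three times baseline and is not flagged.

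**Step 3. The eGFR boundary.** A change of -29.9% is not flagged, correctly. A change of -30.0% is not flagged, although the label counts it. A change of -30.1% is flagged. Only values at exactly -30% are affected, for example a baseline of 20 and a visit value of 14: (14 - 20) / 20 × 100 = -30.

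**Step 4. Would the missed subjects appear elsewhere?** A subject with r above 2 has an eGFR fall of more than 1 - 2^-1.094 = 0.532, or 53%. Ageing during the study only adds to the fall, because the age exponent is negative. Where eGFR and creatinine come from the same samples, these subjects exceed the 30% threshold of Table 2.132. They also exceed the potential clinical importance criterion of a 40% eGFR decrease in section 15.8.1.

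**The case against.** Three arguments deserve an answer.

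**The wording can be read literally.** An increase of more than double might mean that the rise itself exceeds twice baseline, which does give a change above 200%. The SAP never states this reading, and it is a strained one for a doubling measure. If it were intended, the table title would still mislead, so the text would need correcting either way.

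**The display is exploratory.** This stands, and it limits the severity. Section 7.4.1 marks no formal analysis for any CKD display, and section 7.4.5 provides descriptive statistics. The step-down testing in section 5.5 covers only the primary and principal secondary endpoints. The objectives table in section 2.2 does not list either responder count as an endpoint. Table 2.133 is not in the headline deliverable (section 15.10.3).

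**The same information is shown elsewhere.** This also stands. eGFR and creatinine values and changes appear in Tables 2.130 and 2.131, Figures 2.78 and 2.79 and Listing 63. Table 2.132 gives the 30% eGFR count, and Table 3.105 covers the eGFR criterion of clinical importance for the non-dialysis subjects.

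A reader might infer that the tripling cut-off would leave few or no events, or make it look as if neither arm progresses. The documents do not support that. They give no creatinine distribution or event rate from which to forecast a count, and the other displays would still show progression. Nor is it a fault that the creatinine and eGFR flags sit at different severities: a correct doubling flag, at a 53% eGFR fall, would not match the 30% flag either.

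**Conclusion.** The creatinine rule is wrong as written. It identifies more-than-triplings and omits every subject with 2 < r ≤ 3, so Table 2.133 would undercount its named event in both arms. In eGFR terms the flag needs a fall of more than about 70%, where the label implies about 53%. These two figures rest on the SAP's equation with age held fixed; the threshold error itself is algebra and needs no assumption. How many subjects are affected cannot be derived from the document.

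The eGFR boundary is a true but minor mismatch, confined to values at exactly -30%. How often that occurs depends on how eGFR is rounded.

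This is a should-fix. It produces one mislabelled descriptive table and leaves primary and principal secondary conclusions unaffected.

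**What to change.** In section 15.6.6:

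1. Set the creatinine rule to change (%) > 100, which is the same as a visit-to-baseline ratio above 2. Keep the change formula as it is.
2. As a minor alignment, set the eGFR rule to change (%) <= -30.

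Produce Tables 2.133 and 2.132 from the corrected flags. Their titles and the text of section 7.4.2 can stay.

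The cost is two edited thresholds in the SAP and in the derivation program, with no new data. Counts in Table 2.133 can only stay the same or rise; those in Table 2.132 change only if a value falls exactly on the boundary.

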15.6.7. Patient Reported Outcome

The original version of instructions and questionnaire items for the study are written in Japanese. In displays, the items will be translated into English version (can be found at <http://www.qualitymetric.com> for SF-36v2, EuroQol products for EQ-5D-5L).

SF-36v2
Overview of Scoring Algorithm

 • Scores will be calculated by Optum PRO CoRE (version 1.2). Refer to “User’s Manual for the SF-36v2 Health Survey Third Edition” for further details. • Three sets of summary scores will be calculated based on responses to each item on the SF-36: 
 • Physical Component Summary (PCS) score • Mental Component Summary (MCS) score • Domain scores based on the following eight domains 
 • Physical Functioning • Role-Physical (i.e., role limitations due to physical health) • Bodily Pain • General Health • Vitality • Social Functioning • Role-Emotional (i.e., role limitations due to mental/emotional health)

SF-36v2

- Mental Health

The scoring process is summarized in the following figure (Refer to Figure 5.1 in User’s Manual for the SF-36v2 Health Survey Third Edition).

```

graph TD
    S1[Step 1: Enter item response data] --> S2[Step 2: Recode item response values]
    S2 --> S3[Step 3: Determine health domain scale total raw scores]
    S3 --> S4[Step 4: Transform health domain scale total raw scores to 0–100 scores]
    S4 --> S5[Step 5: Transform health domain scale 0–100 scores to T scores using health domain z scores]
    S5 --> S6[Step 6: Score Physical and Mental Component Summary measures using health domain z scores]
    
```

Before submitting an SF-36v2 response set for scoring, the following points will be ensured.

- SF-36v2 Acute is being used for this study. [Acute (1 Week)]
- Missing values will be estimated using the *Maximum Data Recovery Mode*.
- 2009 U.S. general population will be set for scoring. [2009 US Norms]

EQ-5D-5L / EQ-VAS

Scoring Algorithm

- EQ-VAS scores will be summarized based on the numbers subjects have written in the box.
- Index values will be calculated based on responses to each item on the EQ-5D-5L:
 - Mobility (level 1 to 5; e.g., level 1 = “I have no problems in waling about”)
 - Self-Care (level 1 to 5; e.g., level 1 = “I have no problems washing or dressing myself”)
 - Usual Activities (level 1 to 5; e.g., level 1 = “I have no problems doing my usual activities”)
 - Pain / Discomfort (level 1 to 5; e.g., level 1 = “I have no pain or discomfort”)
 - Anxiety / Depression (level 1 to 5; e.g., level 1 = “I am not anxious or depressed”)
- Based on the EQ-5D-5L profile, the index value will be carried out using “EQ-5D-5L_Crosswalk_Index_Value_Calculator.v2” (can be downloaded from the EuroQol website). Japan specific value sets will be used.

15.7. Appendix 7: Reporting Standards for Missing Data

15.7.1. Premature Withdrawals

Element	Reporting Detail
General	
 • Subject study completion (i.e. as specified in the protocol) was defined as follows: A completed subject is one who has completed all periods of the study including the follow-up visit. • Withdrawn subjects were not replaced in the study. • All available data from subjects who were withdrawn from the study will be listed and all available planned data will be included in summary tables and figures, unless otherwise specified. •

15.7.2. Handling of Missing Data

Element	Reporting Detail
General	
 • Missing data occurs when any requested data is not provided, leading to blank fields on the collection instrument: 
 ○ These data will be indicated by the use of a “blank” in subject listing displays. Unless all data for a specific visit are missing in which case the data is excluded from the table. ○ Answers such as “Not applicable” and “Not evaluable” are not considered to be missing data and should be displayed as such.
Outliers	
 • Any subjects excluded from the summaries and/or statistical analyses will be documented along with the reason for exclusion in the clinical study report, if applicable.

15.7.2.1. Handling of Missing and Partial Dates

Element	Reporting Detail
General	
 • Partial dates will be displayed as captured in subject listing displays.
Concomitant Medications/ Medical History	
 • Partial dates for any concomitant medications recorded in the CRF will be imputed using the following convention: 
 ○ When only the start year is provided, a '01' will be used for the day and 'Jan' will be used for the month ○ When only the start month and year is provided, a '01' will be used for the day. ○ When only the stop year is provided, a '28/29/30/31' will be used for the day (dependent on the month and year) and 'Dec' will be used for the month. ○ When only the stop month and year is provided, a '28/29/30/31' will be used for the day (dependent on the month and year) • The recorded partial date will be displayed in listings.
Adverse Events	
 • The eCRF does not allow for the possibility of partial dates.

15.8. Appendix 8: Values of Potential Clinical Importance

15.8.1. Laboratory Values

Chemistry			
Laboratory Parameter	Units	Clinical Concern Range	
		Low Flag	High Flag
Albumin (serum)	g/L	< 30 g/L	>55 g/L
Aspartate Aminotransferase	IU/L	N/A	≥ 3x ULRR
Alanine Aminotransferase	IU/L	N/A	≥ 3x ULRR
Bilirubin (total)	μmol/L	N/A	≥ 2x ULRR
Calcium (albumin-adjusted)	mmol/L	< 1.87 mmol/L	> 2.56 mmol/L
Bicarbonate (total)	mmol/L	< 20 mmol/L	> 32 mmol/L
Inorganic phosphate	mmol/L	< 0.81 mmol/L	> 1.77 mmol/L
Potassium (serum)	mmol/L	> 0.5 mmol/L below LLRR	> 1.0 mmol/L above ULRR
Sodium (serum)	mmol/L	< 130 mmol/L	> 150 mmol/L

Hematology			
Laboratory Parameter	Units	Clinical Concern Range	
		Low Flag	High Flag
Platelet Count	GI/L	< 80 GI/L	> 500 GI/L
WBC Count	GI/L	> 1x LLRR	>5x ULRR
Neutrophils	GI/L	< 1.0 GI/L	N/A
Lymphocytes	GI/L	< 0.5 GI/L	N/A

Iron Parameters			
Laboratory Parameter	Units	Clinical Concern Range	
		Low Flag	High Flag
Ferritin	μg/L	< 100 μg/L	> 1200 μg/L
TSAT	%	<15 %	>40 %

Urinalysis Parameters			
Laboratory Parameter	Units	Clinical Concern Range	
		Low Flag	High Flag
Urine albumin/creatinine ratio	g/mol		> 3.4 g/mol

Other Parameters			
Laboratory Parameter	Units	Clinical Concern Range	
		Low Flag	High Flag
iPTH	ng/L	N/A	> 9x ULRR
eGFR	mL/min/1.73m ²	≥ 40% decrease from baseline	

15.8.2. Vital Signs

Vital Sign Parameter (Absolute)	Units	Clinical Concern Range	
		Lower	Upper
Systolic Blood Pressure	mmHg	< 85 mmHg	> 180 mmHg
Diastolic Blood Pressure	mmHg	< 45 mmHg	> 110 mmHg
Heart Rate	beats/min	< 40 beats/min	> 110 beats/min

